**Additional considerations:**

- Data collected for Parts A1, A2 and B will be pooled for analysis, unless specified otherwise.
- An individual subject data listing will be provided for subjects' visits impacted by COVID-19.

All individual subject data will be presented in individual subject data listings based on the All Subjects Set.

## **9.2 Background Characteristics**

### **9.2.1 Subject Disposition**

Disposition summary will be provided by treatment group and overall.

The number of subjects, based on the All Subjects Set, in the following disposition categories, will be summarized:

- All Subjects Set
- Full Analysis Set
- Safety Set
- Randomized
- Randomized but not dosed

The number and percentage of subjects, based on the FAS, in each of the following disposition categories, will be summarized:

- Completed treatment
- Discontinued treatment and the reason for discontinuation from treatment
- Completed study
- Discontinued study and the reason for discontinuation from study

### **9.2.2 Demographics and Baseline Characteristics**

Demographics and baseline characteristics will be summarized based on the FAS by treatment group and overall.

Demographic data will include the following:

- Age (in years)
- Sex (female and male)
- Ethnicity (Hispanic or Latino, not Hispanic or Latino, and not collected per local regulations)
- Race (White, Black or African American, Asian, American Indian or Alaska Native, Native Hawaiian or Other Pacific Islander, Other, and Not Collected per Local Regulations)

Baseline characteristics will include the following:

- Weight (kg)
- Height (cm)
- BMI (kg/m^2)
- Prior Augmentation Therapy (Yes, No)
- Smoking History (Yes, No)
- ppFEV1 category determined during the Screening Period or from historical data (< 50%, ≥50%)
- ppFEV1 obtained during the Screening Period or from historical data (%)
- FEV1 obtained during the Screening Period or from historical data (L)
- FVC obtained during the Screening Period or from historical data (L)
- Ratio of FEV1 and FVC obtained during the Screening Period or from historical data (%)
- Functional AAT level (μM)

- Antigenic AAT level ( $\mu\text{M}$ )

### 9.2.3 Medical History

Medical history will be coded by using the Medical Dictionary for Regulatory Activities (MedDRA). Medical history will be summarized descriptively based on the FAS by MedDRA system organ class (SOC) and preferred term (PT). This summary will be provided by treatment group and overall.

### 9.2.4 Prior and Concomitant Medications

Medications will be coded using the World Health Organization-Drug Dictionary (WHODrug) and categorized as the following for the purpose of analysis:

**Prior medication:** Medication that started before the first dose of study drug

**Concomitant medication:** Medication continued or newly received during the TE Period

**Post-treatment medication:** Medication continued or newly received after the TE period

A given medication may be classified as a prior medication, a concomitant medication or both a prior and a concomitant medication.

If a medication start date is on or after the first dose date of study drug, then the medication will be classified as concomitant medication regardless of whether the medication end date is missing or not. If a medication end date is before the first dose date of study drug, then the medication will be classified as prior medication regardless of whether the medication start date is missing or not. Note that medication that started before the first dose of study drug and continued after the first dose will be classified as prior medication and separately as concomitant medication.

If a medication has a missing or partially missing start/end date and it cannot be determined whether it was taken before the first dose of study drug, or concomitantly, it will be classified as prior and concomitant medication.

Missing or partial dates will be imputed for medication. Details for imputing missing or partial start and/or stop dates of medication are described in Appendix B.

Prior medications will not be summarized but will only be listed. Concomitant medications will be summarized based on the FAS by PT. This summary will be provided by treatment group and overall of VX-814 treatment groups. Bronchodilator will also be listed.

Prior and concomitant non-drug therapy will be listed.

### **9.2.5 Study Drug Exposure and Compliance**

Study drug exposure (in days) will be calculated as (last date of dosing – first date of dosing) + 1, regardless of study drug interruption, and will be summarized descriptively based on the Safety Set by treatment group and overall. It will also be summarized in categories:  $\leq 7$  days,  $> 7$  to  $\leq 14$  days,  $> 14$  to  $\leq 21$  days,  $> 21$  to  $\leq 28$  days, and  $> 28$  days, using counts and percentages.

Study drug compliance will be calculated as  $100 \times [1 - (\text{total number of days of study drug interruption}) / (\text{duration of study drug exposure in days})]$ . A study drug interruption on a given day is defined as any interruption of the study drug on that day. A study drug interruption that continues through the end of study participation (i.e., subject does not resume study drug before the end of study participation) will not be included in the compliance calculation. Study drug compliance will be summarized descriptively based on the FAS by treatment group and overall. It will also be summarized in categories:  $< 80\%$  and  $\geq 80\%$ , using counts and percentages.

### **9.2.6 Important Protocol Deviations**

An important protocol deviation (IPD) is a deviation that may significantly affect the completeness, accuracy, or reliability of the study data or that may significantly affect a subject's rights, safety, or well-being. IPD rules will be developed and finalized before the clinical database lock. IPDs will be identified by the PD review team according to the protocol deviation plan.

[figure not shown]
IPDs will be summarized descriptively based on the FAS by treatment group and overall.

## **9.3 Efficacy Analysis**

All efficacy analyses described in this section will be based on the FAS, unless otherwise specified. Subjects will be analyzed according to the treatment to which they were randomized.

### **9.3.1 Analysis of Primary Efficacy Variable**

The primary efficacy variable is the change from baseline in plasma functional AAT levels at Day 28.

The observed values and change from baseline of functional AAT levels will be summarized descriptively by treatment group at each visit. The treatment differences of VX-814 400 mg q12h versus placebo and VX-814 600 mg q12h versus placebo in change from baseline of functional

AAT levels at Day 28 will be provided. If the sample size allows, the 2-sided  $P$  values and 95% confidence intervals of the treatment differences will also be provided based on the two-sample  $t$  test.

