9.3 Method of Assigning Subjects to Treatment Groups

In Part A1, subjects will be randomized (2:1:1:1) to 1 of 3 VX-814 groups or to the placebo group. In Part A2, subjects will be randomized (3:1) to the VX-814 group or to the placebo group. In Part B, subjects will be randomized (3:1) to the VX-814 group or to the placebo group. Each randomized subject will be assigned a unique subject number. Randomization will be stratified by ppFEV₁ obtained either during the Screening Period or from a historical ppFEV₁ value (<50% versus ≥50%).

An interactive web or voice response system (IWRS) will be used to assign subjects to treatment. The randomization code will be produced by Vertex Biostatistics or a qualified randomization vendor. The Vertex study biostatistician will review and approve the production of the final randomization list, which will be reviewed and approved by a designated unblinded biostatistician who is not a member of the study execution team (SET).

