12.3.2 Demographics and Background Characteristics

Subject disposition, e.g., completed treatment, prematurely discontinued the treatment and the reason for discontinuation, will be summarized by treatment group.

Demographic and other baseline characteristics (e.g., plasma AAT levels and ppFEV₁) will be summarized by treatment group. No statistical tests will be carried out to evaluate baseline imbalances between treatment groups.

Medications used will be coded using the World Health Organization-Drug Dictionary (WHODrug) and summarized descriptively. Exposure to study drug (i.e., duration of treatment) and dosing compliance (i.e., percentage of days being compliant to treatment) will be summarized descriptively.

Important protocol deviations will be provided in an individual subject data listing, and summarized, as appropriate.

Additional details will be provided in the SAP.

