12.3.3.3 Missing Data Handling

For the primary analysis of the primary endpoint, missing data will be assumed to be missing at random conditional on the observed data and covariate; consequently, no imputation of missing data will be performed.

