## 7.2 Sample Size and Power

Approximately 43 subjects in total will be randomized to both parts of the study. In Part A1, subjects will be randomized to receive VX-814 400 mg q12h (n = 6), VX-814 200 mg q12h (n = 3), VX-814 100 mg q12h (n = 3), or placebo (n = 3). In Part A2, subjects will be randomized to receive VX-814 400 mg q12h (n = 6) or placebo (n = 2). In Part B, subjects will be randomized to receive VX-814 600 mg q12h (n = 15) or placebo (n = 5).

Assuming approximately 10% of the randomized subjects have a missing value at Day 28, this sample size provides adequate precision to estimate the plasma functional AAT levels at Day 28 for the VX-814 600 mg q12h group in Part B.

Information regarding the sample size assessments is provided below.

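### The conditional P values and confidence intervals for AAT change come from an unadjusted t test; adjusting for baseline AAT and the ppFEV1 stratum is a cheap, possible but not guaranteed precision gain

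*SAP*

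**What the plan says.** SAP 9.3.1 always gives descriptive summaries and the differences of 400 mg and 600 mg from placebo in Day 28 change of functional AAT. Inference is conditional. It opens with "If the sample size allows, the 2-sided" and continues that P "values and 95% confidence intervals of the treatment differences will also be provided based on the two-sample" t test. SAP 9.3.2 repeats this for antigenic AAT. Neither section names a covariate or stratum.

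The two obvious candidates are already in the data:

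- Protocol 9.3: "Randomization will be stratified by ppFEV₁ obtained either during the Screening Period" or from a historical value, cut at 50%.
- Protocol 12.3.2: "Demographic and other baseline characteristics (e.g., plasma AAT levels and ppFEV₁) will be summarized by treatment group".
- SAP 9.2.2 lists the ppFEV1 "category determined during the Screening Period or from historical data", together with both AAT levels.

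Three other places bear on the point:

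- SAP 9.1: "Data collected for Parts A1, A2 and B will be pooled for analysis, unless specified otherwise".
- Protocol 12.3.3.3, for the primary analysis: "missing data will be assumed to be missing at random conditional on the observed data and covariate".
- SAP 7.2 claims "adequate precision to estimate the plasma functional AAT levels at Day 28 for the VX-814 600 mg q12h group in Part B".

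The model text in Protocol 12.3.3.1 is redacted, so only the visible SAP text can be judged.

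**The concern.** A t test on change subtracts baseline with a coefficient fixed at 1. ANCOVA estimates that coefficient and so never has a larger residual variance in large samples. Leaving out the randomization stratum also keeps any variation due to ppFEV1 in the error term. With about 15, 12 and 10 subjects in the 600 mg, 400 mg and pooled placebo groups, the intervals are wide. Data already held might narrow the only formal comparisons that the SAP offers. What is at stake is chiefly precision. The open questions are how large the gain is, and whether it is a gain at all.

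**Working it through.** **1. Group sizes (SAP 7.2, pooled under SAP 9.1).** Part totals are 15 + 8 + 20 = 43, which matches the plan. Placebo: 3 + 2 + 5 = 10. 400 mg: 6 + 6 = 12. 600 mg: 15. The visible text gives no SD, correlation, power or target width, so there is no precision figure to reproduce.

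**2. Planned t interval.** Half-width in SDs of change = t(0.975, n1+n0-2) x sqrt(1/n1 + 1/n0).

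- 600 mg, 15 v 10: 2.069 x 0.408 = 0.84. With about 10% missing (13 v 9): 0.90.
- 400 mg, 12 v 10: 2.086 x 0.428 = 0.89. With about 10% missing (11 v 9): 0.94.

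**3. Large-sample gain from baseline.** Let baseline SD be 1, Day 28 SD be k, and their correlation be rho.

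- Variance of change: k² + 1 - 2k·rho.
- ANCOVA residual variance: k²(1 - rho²).
- Difference between the two: (1 - k·rho)².

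The gain is therefore zero when k·rho = 1. With equal SDs (k = 1), the width ratio is sqrt((1 + rho)/2).

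**4. Small-sample cost.** Two covariates cost two degrees of freedom (critical t 2.069 to 2.080 for 600 mg, 2.086 to 2.101 for 400 mg) plus chance covariate imbalance. I simulated the three-Part design. The assumptions were permuted blocks within stratum and Part, 40% of subjects below 50% ppFEV1, no stratum effect, data missing completely at random, and 4,000 trials per cell. Change in mean 95% CI width, ANCOVA with both terms against the t test, k = 1:

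| | rho 0.3 | 0.5 | 0.7 | 0.9 | 0.999 |
|---|---|---|---|---|---|
| Large-sample ratio | 0.806 | 0.866 | 0.922 | 0.975 | 1.000 |
| 600 mg, complete | -17% | -10% | -5% | +1% | +3% |
| 400 mg, complete | -16% | -10% | -4% | +2% | +4% |
| 600 mg, 10% missing | -16% | -10% | -4% | +2% | +4% |
| 400 mg, 10% missing | -15% | -9% | -3% | +2% | +5% |

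At rho near 1 with equal SDs, baseline adds nothing, so the last column is the cost when both terms are useless. As a check, SD of change at rho 0.7 is sqrt(0.6) = 0.775. Then 0.8445 x 0.775 = 0.654 baseline SDs, against a simulated mean t half-width of 0.648 (ANCOVA 0.618).

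These are averages. At rho 0.7 the adjusted interval was the wider one in 36-43% of trials.

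**5. Where the gain vanishes or reverses.**

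- *Larger spread at Day 28* (600 mg, complete data; rho 0.3 / 0.5 / 0.7 / 0.9). k = 1.5: -4 / +2 / +3 / -9%. k = 2: +1 / +3 / -1 / -24%. At k = 1.5 and rho 0.7, (1 - 1.05)² = 0.0025 out of a variance of 1.15, so almost nothing is gained to offset the cost. The entry limit of 8 µM on antigenic AAT (Protocol 8.1, criterion 7) makes a narrower baseline spread possible.
- *Extra response variation of 1 baseline SD in the active arm only*, same four rho values: -10 / -5 / 0 / +3%.
- *Fewer subjects.* With 25% missing (600 mg): -14 / -8 / -2 / +4%. With half analysable, at rho 0.7 to 0.9: +4% to +12% (600 mg) and +7% to +17% (400 mg).

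**6. Break-even and the stratum term.** A second simulation, with 10% missing and 50:50 strata, varied the share of variance of change explained. Break-even for both terms is about 9%. With equal SDs and a non-prognostic stratum, (1 - rho)/2 = 0.09 gives rho of about 0.82. When it does not predict change, the stratum term costs about 1 to 1.5 points of width (0.7 to 1.8 in single cells). For 600 mg at rho 0.7 with 10% missing, baseline alone gives -4.9% and both terms give -3.6%. If the stratum correlates 0.3 with change, it helps: the width ratio for 600 mg is 0.991 with both terms against 1.029 with baseline alone.

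**7. Validity.** With no Part effect and 0 to 10% missing, type I error was 4.2-5.5% (t test) and 4.4-5.7% (ANCOVA). With a prognostic stratum, the t test rejected in 3.9-4.9% of null trials, so it is if anything slightly conservative.

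**The case against.** The strongest reply is that nothing here is wrong. The t test on change matches the stated endpoint, holds its error rate, and supplements a mainly descriptive analysis. No visible text sets a width or power target for the difference. The sign of the gain is uncertain as well as its size. No passage shows that ppFEV1 predicts AAT change, and if it does not, baseline alone does better. When numbers are small, the SAP already limits inference.

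Most of this stands, and it is why the point is an improvement and not a defect. Two things remain. First, near planned size the possible outcomes are lopsided under equal SDs: at most about 5% wider, against up to 17% narrower. Second, the precision case rests mainly on baseline AAT. The stratum is included because randomization used it, not because a benefit has been shown.

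A reader might infer that the SAP departs from a covariate-adjusted model in the protocol, since Protocol 12.3.3.3 mentions a covariate and the abbreviation list contains MMRM. The documents do not support that, because Protocol 12.3.3.1 is redacted and the planned model cannot be seen. What can be said is that a covariate-adjusted SAP analysis would fit the visible wording of 12.3.3.3 better. In a deliberately adverse case, with 10% missing driven by baseline in opposite directions in the two arms, the t-test difference was biased by 0.05 to 0.09 SD. ANCOVA bias was about 0, and the t test's type I error stayed at 5.0-5.2%.

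**Conclusion.** The point holds as a minor suggestion. The visible inference is a valid but unadjusted t test, and adjustment is cheap and may narrow the interval. Under equal SDs and near planned size, the mean width with both terms changes by -17% to -15% at rho 0.3, -5% to -3% at rho 0.7 and +1% to +2% at rho 0.9. It is 3-5% wider if neither term helps. The correlation, the SDs and the share of subjects below 50% ppFEV1 are all assumed, and the documents give none of them.

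Three stronger readings are not supported:

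- *The t test is invalid because it ignores the stratification.* Its error rate is held, as shown above.
- *Adjustment is sure to help.* A larger Day 28 spread or numbers far below plan can remove or reverse the gain.
- *The precision claim in SAP 7.2 fails.* That claim concerns the 600 mg group in Part B alone and sets no target for a difference from placebo.

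Adjustment also does not deal with a Part effect from pooled placebo. With an assumed Part B shift of 0.5 SD of change at rho 0.7, half the placebo group is unshifted, so both methods are biased by about 0.5 x 0.775 x 0.5 = 0.19 baseline SD. Type I error is then 8.4% (t test) and 8.9% (ANCOVA).

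**What to change.** Before database lock, amend SAP 9.3.1 and 9.3.2:

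- Where inference is given near planned size, base the difference, 95% CI and P value on ANCOVA of Day 28 change. The terms are treatment and the baseline value of the same AAT measure, fitted to the two groups compared.
- Include the ppFEV1 stratum (below 50% or not) because randomization is stratified by it. Note that its predictive value for AAT change is not shown.
- Keep the unadjusted difference and t interval as a supportive line.
- If analysed numbers fall well below plan, keep the t test or the descriptive summary, and fix that switch in advance. As an example only, a rule of at least 8 per arm would use ANCOVA in about 88% of simulated trials at 10% missing (600 mg: -14 / -8 / -3 / +1% at rho 0.3 / 0.5 / 0.7 / 0.9). At half size it would use ANCOVA in 1-4% of trials, and mean width would change by no more than 0.3%.

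The cost is SAP wording and a few lines of code, with no new data. The statistical cost is two residual degrees of freedom and, if the stratum is not prognostic, about 1 to 1.5 points of width.

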9.4 Rationale for Study Elements

9.4.1 Rationale for Study Design

A parallel-group, randomized, placebo-controlled design was selected to minimize the imbalance in the distribution of the baseline characteristics of the different dosing groups. A double-blind design was included to prevent bias in endpoint assessment by the investigator or subject.

The 28-day treatment duration is based on the estimated plasma half-life for AAT of approximately 5 days, indicating that plasma AAT levels will reach >95% of steady-state levels by the end of the treatment period. Therefore, it is expected that the 28-day treatment duration of VX-814 will be sufficient to evaluate the maximal effect of each dose level on plasma AAT.

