9.8 Dose Modification for Toxicity

No dose modifications for toxicity are allowed or required. If any unacceptable toxicity arises in the opinion of the investigator individual subjects will discontinue dosing (Section 9.1.4).

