10.7.1 Blinding

All subjects, site personnel (including the investigator, the site monitor, and the study team), and the Vertex study team will be blinded to the treatment codes with the exception of the following:

- Any site personnel for whom this information is important to ensure the safety of the subject in the event of a life-threatening medical emergency
- Any site personnel for whom this information is important to ensure the safety of the subject and her fetus in the event of a pregnancy
- Vertex GPS and Regulatory Affairs personnel to satisfy SAE processing and reporting regulations
- Unblinded statistician preparing the final (production) randomization list who is not part of the study team
- Vertex IWRS Manager
- Vertex Clinical Supply Chain
- The bioanalytical CRO analyzing PK samples and the Vertex Bioanalytical personnel who is not a member of the SET but analyzes and reviews raw data from Bioanalytical CRO. The Vertex Bioanalytical SET member will continue to be blinded.

Vertex medical monitor may, for matters relating to safety concerns, unblind individual subjects at any time.

A limited Vertex team not directly involved in the conduct of the study may be unblinded to individual subject treatment assignments and have access to plasma AAT levels, PK, and/or safety data (e.g., adverse events, clinical laboratory assessments) for continuous monitoring purposes. No unblinded data or results of unblinded analyses will be shared with the study sites or with the Vertex study team. All instances of unblinding by Vertex personnel will be documented.

Access to results of plasma functional and antigenic AAT data:

During the conduct of the study, the Vertex study team will not have access to the plasma AAT level results until the study is unblinded for full review, with the exception of the screening plasma antigenic AAT levels. Antigenic AAT levels obtained during screening will be provided to study sites in order to confirm the subject's eligibility to enroll in the study. Other AAT level results will not be disclosed to the study sites.

Shortly before any planned efficacy analysis related to plasma AAT levels is conducted, plasma AAT data will be reviewed for data cleaning purposes by a biostatistician who does not have access to the treatment codes.

Access to direct and indirect bilirubin results

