12.1 Sample Size and Power

Approximately 43 subjects in total will be randomized to both parts of the study. In Part A1, subjects will be randomized to receive VX-814 400 mg q12h (n = 6), VX-814 200 mg q12h (n = 3), VX-814 100 mg q12h (n = 3), or placebo (n = 3). In Part A2, subjects will be randomized to receive VX-814 400 mg q12h (n = 6) or placebo (n = 2). In Part B, subjects will be randomized to receive VX-814 600 mg q12h (n = 15) or placebo (n = 5).

Assuming approximately 10% of the randomized subjects have a missing value at Day 28, this sample size provides adequate precision to estimate the plasma functional AAT levels at Day 28 for the VX-814 600 mg q12h group in Part B.

Information regarding the sample size assessments is provided below.

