12.3 Statistical Analysis

The primary objective of this study is to characterize the efficacy and safety of VX-814 in *PiZZ* subjects. This section summarizes the statistical analysis of efficacy and safety data.

Methodological and related details (e.g., missing data) will be in the SAP.

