for subjects who do not have a Safety Follow-up Visit 14 days after the last dose of study drug or an equivalent ETT.

**Unscheduled visits:** Data obtained from unscheduled visits will be included in the analysis as follows:

- In scheduled visit windows per specified visit windowing rules
- In the derivation of baseline and last on-treatment measurements
- In the derivation of maximum and minimum values during TE period, and maximum and minimum change from baseline values during TE period for safety analyses
- In individual subject data listings as appropriate

**Incomplete or missing data** will not be imputed, unless specified otherwise.

**Outliers:** No formal statistical analyses will be performed to detect and/or remedy the presence of statistical outliers, unless specified otherwise.

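### The Day 28 comparison in SAP 9.3.1 does not use the earlier AAT values or the ppFEV1 stratum, so the protocol's missing-at-random assumption does not protect it

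*SAP*

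**What the plan says.** SAP 9.3.1 summarizes functional AAT descriptively at each visit. It then gives the difference in Day 28 change for 400 mg versus placebo and for 600 mg versus placebo. If the sample size allows, P values and "95% confidence intervals of the treatment differences will also be provided based on the two-sample" t test are added. SAP 9.3.2 does the same for antigenic AAT. Baseline AAT enters only by subtraction, and no other covariate or visit enters the comparison.

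Protocol 12.3.3.3 states that for the primary analysis "missing data will be assumed to be missing at random conditional on the observed data and covariate", and concludes that no imputation is needed. Protocol 12.3 says that "Methodological and related details (e.g., missing data) will be in the SAP". On this the visible SAP says only, in 9.1, that incomplete or missing data "will not be imputed, unless specified otherwise".

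Protocol Table 3-3 schedules functional and antigenic AAT on Days 1, 7, 14 and 28. Protocol 9.3 stratifies randomization by ppFEV1 (below 50% versus 50% or more). The sample size sections of both documents plan on some loss: "Assuming approximately 10% of the randomized subjects have a missing value at Day 28".

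**The concern.** Missing at random given observed data justifies leaving values unimputed only when the analysis conditions on those data, as a likelihood model of all visits does. A difference in observed Day 28 means needs more: either loss unrelated to outcome within each arm, or selection that cancels between arms. The protocol's assumption guarantees neither.

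Any link between AAT and loss must be indirect, because after screening "Other AAT level results will not be disclosed to the study sites". One possible route is exposure that drives both AAT response and toxicity, since under Protocol 9.8 "individual subjects will discontinue dosing" when toxicity is unacceptable. The documents do not establish such a link and fix neither the size nor the direction of a bias.

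How many Day 28 values will be missing is also unclear. Protocol 9.1.2 has subjects who stop drug early complete assessments at all study visits and refers to 9.1.4 for the description, but 9.1.4 names only an early-termination visit and the Safety Follow-up Visits.

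At stake is the primary efficacy estimate, from 15 versus 10 and 12 versus 10 subjects. At those sizes a few selective losses can move it.

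**Working it through.** **Inputs from the documents.** The arms in SAP 7.2 are 6 + 3 + 3 + 3 + 6 + 2 + 15 + 5 = 43, which agrees with 15 + 8 + 20 = 43. Parts are pooled (SAP 9.1), so placebo is 3 + 2 + 5 = 10, 400 mg is 6 + 6 = 12 and 600 mg is 15. The claim of adequate precision cannot be reproduced, because no SD or target half-width is visible. All results below are therefore in units of the SD of change.

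**Expected loss.** 0.10 × 43 = 4.3 subjects. If all are on active drug, 4.3/33 = 13%. If all are on 600 mg, 4.3/15 = 29%, an extreme case.

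**Half-width with complete data.**
- 600 mg: t(0.975, 23) × √(1/15 + 1/10) = 0.84 SD.
- 400 mg: t(0.975, 20) × √(1/12 + 1/10) = 0.89 SD.

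**Size of the bias.** Assume a true difference of zero, loss on active drug only, Day 14 and Day 28 changes bivariate normal with correlation ρ from 0.5 to 0.9, and a logistic probability of loss in the Day 14 change with slope 0.5, 1 or 2 per SD. Let π be the fraction lost and m the mean Day 14 change of those lost, in SD from the arm mean. The mean Day 14 change of those who remain is shifted by −mπ/(1 − π), so

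|bias| = ρ × m × π/(1 − π).

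Numerical integration at 10% loss gives m = 0.44, 0.82 and 1.28 for the three slopes. At slope 2 and ρ = 0.9, for example, 0.9 × 1.28 × 0.111 = 0.13 SD. At 29% loss and slope 2, m = 0.90, and 0.9 × 0.90 × 0.402 = 0.33 SD.

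Simulation (40,000 trials per setting, pooled t test, 600 mg versus placebo) agrees. Each cell gives absolute bias in SD and type I error over the range of ρ:

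| Loss on active | Slope 0.5 | Slope 1 | Slope 2 |
|---|---|---|---|
| 10% | 0.02–0.04 (4.8–5.3%) | 0.04–0.08 (5.1–5.4%) | 0.07–0.13 (5.5–6.2%) |
| 13% | 0.03–0.06 (5.1–5.4%) | 0.06–0.10 (5.3–5.8%) | 0.09–0.16 (5.7–6.7%) |
| 29% | 0.07–0.12 (5.3–5.7%) | 0.12–0.22 (6.0–7.6%) | 0.18–0.33 (6.8–11.7%) |

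Monte Carlo SE is 0.002 SD for bias and 0.1 points for type I error. The sign is set by whether high or low responders are lost. For 400 mg versus placebo at 10% loss the bias is 0.03 to 0.13 SD (5.0 to 5.7%). The 600 mg half-width is 0.83 to 0.87 SD at 10 to 13% loss and 0.86 to 0.91 SD at 29%.

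**When it vanishes.** Purely random loss of 30% versus 0% gives bias 0.00 SD and type I error 5.0%. Identical selection in both arms (10%, slope 2) gives the same.

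**Stratum alone.** With equal strata and 30% of the lower stratum lost in one arm only, that stratum's share of observed subjects is 0.35/0.85 = 0.41. A stratum effect of 0.3 to 0.5 SD then gives (0.50 − 0.41) × 0.3 to 0.5, about 0.03 to 0.04 SD.

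**Model on the same problem.** This was change at Days 7, 14 and 28 fitted by REML with treatment × visit, baseline, stratum and unstructured covariance (3,000 trials per setting; Monte Carlo SE 0.007 to 0.011 SD and 0.4 points). For 600 mg versus placebo:
- 10% loss, slopes 0.5 to 2: |bias| at most 0.02 SD, type I error 4.2 to 5.8%, median half-width 0.81 to 0.82 SD.
- 29% loss, slope 2: |bias| at most 0.01 SD, 4.6 to 4.8%, 0.82 to 0.85 SD.
- Arms of 5, 6 and 8 (placebo, 400 mg, 600 mg), 10% loss, slopes 1 to 2: |bias| at most 0.02 SD, 4.8 to 5.5%, 1.22 to 1.23 SD (t test 1.22 to 1.26 SD).

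The unstructured fit converged in every simulated trial.

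**The case against.** The strongest reply is that the effect is small where the plan expects to be. At 10% loss the bias is at most 0.13 SD against a half-width near 0.85 SD, and the type I error ranges of the two methods largely overlap. The study is sized for estimation, P values and intervals are conditional on sample size, and a simple comparison is defensible with 10 to 15 subjects per arm. This stands, and it limits the severity.

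The model also has costs. If active arms are more variable (SD 1.5 times placebo, 10% loss), its type I error falls to 2.9 to 3.4% while the t test holds 4.2 to 5.2%. In the same settings, however, the model's bias stays within 0.01 SD and the t test's is 0.11 to 0.17 placebo SD. No fallback covariance was simulated, and the simulation paired the Kenward-Roger variance with Satterthwaite-type degrees of freedom.

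The simulated loss suits the model, because only Day 28 is lost and its cause, the Day 14 value, is always observed. A subject who stops before Day 14 may lack that value, and loss that depends on it is then not missing at random. This stands as a limit of any missing-at-random analysis.

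Finally, Protocol 12.3.3.1 is partly redacted, MMRM is in the protocol's abbreviation list, and the SAP's visit windowing rules are not visible. A supportive model, or early-termination values mapped to Day 28, cannot be excluded. SAP 9.3.1 itself shows no redaction and names its method. Days 7 and 14 do appear in its descriptive summaries, but not in the treatment comparison.

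**Conclusion.** The concern holds. The comparison visible in SAP 9.3.1 and 9.3.2 needs a stronger condition than the missing-at-random assumption in Protocol 12.3.3.3. If AAT-related loss differs between arms it is in general biased. Under the assumed mechanism the bias is 0.02 to 0.13 SD at the planned 10% loss and 0.18 to 0.33 SD only with 29% loss and the steepest slope. Size and sign rest on assumed correlation, slope and allocation of loss, none of which the documents give. It should be fixed because the estimate is primary and the data that remove the bias under the protocol's own assumption are already collected. It does not invalidate the trial.

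**What to change.** In SAP 9.3.1 and 9.3.2, estimate the Day 28 differences for 400 mg and 600 mg versus placebo with a likelihood-based repeated-measures model of change at Days 7, 14 and 28. Include treatment, visit, treatment × visit, baseline AAT and ppFEV1 stratum. Use unstructured covariance, a simpler structure named in advance as fallback, and Kenward-Roger degrees of freedom. Leave the two arms of 3 descriptive. Keep the raw difference and t test as supportive, which also covers unequal variances.

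State whether AAT values taken after stopping study drug enter the model. Protocol 9.4.1 gives an "estimated plasma half-life for AAT of approximately 5 days". With simple first-order decay, 2^(−7/5) = 38% of an on-drug rise remains 7 days after the effect ends and 2^(−14/5) = 14% after 14 days, so the choice changes what is estimated.

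Separately, reconcile Protocol 9.1.2 with 9.1.4 on whether a Day 28 AAT sample is taken after early stopping.

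The cost is SAP wording and programming, with no new data. The model has 3 × 3 + 2 = 11 fixed effects and 6 covariance parameters for 10 + 12 + 15 = 37 subjects. Real data may need the fallback, and the result still relies on missing at random.
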